## **10.4 Statement on medical justifiability**

Based on previous experience with compression therapy and MRI the risk of occurrence of unwanted events is stratified as extremely low.

## **11 Biometrics**

Continuous variables are given as means with standard deviation. Categorial variables are given as frequencies and percentage. Although making use of a crossover design, we do not expect any carryover or period effects due to the nature of the treatments. Therefore, differences between the treatments and baseline measurements are evaluated using Wilcoxon signed rank tests. Moreover, linear regression analysis is used to adjust for variations in

baseline measurements for the direct comparison of compression classes. A p-value below or equal to 0.05 is considered to indicate statistical significance.

All results will be calculated using R version 3.5.1 (R Foundation for Statistical Computing, Vienna, Austria).

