## 5 Study objectives

The aim of this study is to prove a therapeutic effect of compression therapy using flat-knitted compression stockings on venous malformations of the extremities and to derive from this a therapy recommendation in connection with an improvement in the health status and quality of life.

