**Primary objective:**

- Determination of volume difference of the malformation by use of non-invasive measurements (Perometry, MRI)

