## 6 Target parameters

### 6.1 Primary target:

- Volume of affected extremity(ml)
  - *This target is measured non-invasively by perometry and MRI*

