### 6.2 Secondary targets:

- Volume of affected extremity immediately after application of compression (ml)
  - *This target is measured non-invasively by perometry and MRI*
- Quality of life by SF-12 (short form 12) questionnaire
- Handling and wearing comfort of compression stockings in everyday life by questionnaire "*Tragekomfortbogen*" (comfort of wearing questionnaire)

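### Does summarising limb volume in ml, with no percent change or confidence interval and no stated regression scale, call for a change to the analysis plan?

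*Combined protocol and SAP*

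**What the plan says.** Sections 6.1 and 6.2 define the volume targets for the affected extremity in ml, by perometry and MRI. The primary objective in section 5.1 and the list in section 9.3 refer instead to the volume of the malformation.

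Section 11 is the whole statistical plan. On this point it says:

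- Summary: "Continuous variables are given as means with standard deviation".
- Comparison with no stocking: "differences between the treatments and baseline measurements are evaluated using Wilcoxon signed rank tests".
- Class I against class II: "linear regression analysis is used to adjust for variations in" baseline. The outcome variable and its scale are not named.
- Threshold: "A p-value below or equal to 0.05 is considered to indicate statistical significance".

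Section 8.2 plans about 25 patients aged 6-70 with upper or lower limb lesions, and section 8.1 admits any local extent. On day 28 (section 9.2) each patient is measured without a stocking and then with each class. Section 5 aims to "derive from this a therapy recommendation in connection with an improvement in the health status and quality of life".

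**The concern.** Limb volume will vary several-fold in this population. If compression removes a roughly constant fraction of volume, the mean change in ml mostly reflects the largest limbs. It then describes neither a child's arm nor an adult's leg. A mean, an SD and a p-value also do not state how precisely the effect is known, and the trial is meant to support a therapy recommendation.

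The regression raises a separate worry. If its scale is chosen after the data are seen, the class comparison could depend on that choice. A relative measure would need no new data, since the no-stocking reading is already taken.

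**Working it through.** **Inputs.** From the documents: about 25 patients, mixed limbs, three day-28 readings per patient, 0.05 threshold. The documents give no volumes, SDs, effect size or measurement error. Assumed: arm/leg volumes of 3000/7000 or 2000/8000 ml, 20-50% arms, and various error structures. There is no planned figure to reproduce.

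**1. If the change is proportional.** Mean ml change = 0.05 × (p × arm + (1 − p) × leg) for a uniform 5% change, where p is the share of arms.

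| Arm/leg (ml) | Arms | Mean change (ml) | % of arm | % of leg | Leg share of change |
|---|---|---|---|---|---|
| 3000/7000 | 20% | 310 | 10.3 | 4.4 | 0.90 |
| 3000/7000 | 50% | 250 | 8.3 | 3.6 | 0.70 |
| 2000/8000 | 20% | 340 | 17.0 | 4.3 | 0.94 |
| 2000/8000 | 50% | 250 | 12.5 | 3.1 | 0.80 |

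Here the ml mean transfers poorly.

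**2. If the change is constant in ml.** Take 200 ml in every patient, 2000/8000 ml limbs and 30% arms. That is 200/2000 = 10% of an arm and 200/8000 = 2.5% of a leg. The mean percentage is 0.3 × 10 + 0.7 × 2.5 = 4.75%, which describes neither limb. The ml mean is 200 for everyone, and legs contribute exactly their 70% share of patients. A mean in ml leans towards large limbs only if the change grows with limb volume, and the documents do not say that it does.

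**3. The planned tests.** Exact signed-rank test, n = 25, simulated:

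- Null rejection is 4.7-5.0% on both scales.
- Power with proportional noise (2% reduction, 4% noise), ml against log ratio, in three limb mixes: 61.9 v 66.0, 59.0 v 65.9, 57.7 v 65.6. With a 3% reduction and 5% noise the pattern is the same, so the log ratio gains 4 to 8 points.
- Power with 150 ml error per reading (2% reduction): 78.1 v 70.2, 76.4 v 58.0, 56.9 v 36.7. With 2% noise added: 64.1 v 58.4, 60.2 v 46.5, 45.3 v 31.2. The log ratio loses 6 to 20 points.

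**4. The class regression.** Take one reading of section 11: the class II minus class I difference regressed on centred no-stocking volume, with the intercept tested on 23 df. Type I error at nominal 5%:

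| Error | ml | log |
|---|---|---|
| Proportional | 5.0-6.9% | 4.8-5.2% |
| Constant ml | 4.8-5.2% | 5.5-8.6% |

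The excess comes from adding the covariate when the error variance is unequal. A paired t-test without it holds 4.4-5.3% on ml and 3.9-5.2% on log. Always taking the smaller p-value of the two scales would give 6.3-11.0%.

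**5. The interval.** With 25 pairs the 95% half-width is 2.064 × SD/√25 = 0.413 × SD of the paired change. For an SD of 3, 5 or 10 percentage points that is 1.2, 2.1 or 4.1 points. It needs only the paired readings already planned.

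**6. The denominator.** Suppose a 100 ml lesion empties completely. That is 100/2000 = 5% of an arm, 100/8000 = 1.25% of a leg, and 100% of the lesion. The ml figure is the same in all three.

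**The case for a change.** The strongest case for a change is that section 11 gives no effect estimate with its precision and leaves the outcome of the class regression open. The remedy would be a few sentences, with no new measurement or test. A scale fixed in advance is more credible than one chosen later, and 6.3-11.0% shows what free choice could cost. Baseline adjustment does not settle it, because one additive ml class effect across arms and legs is itself an assumption. Section 11 also does not say how the regression respects the pairing of two readings per patient.

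As description, all of this stands. It does not show that the plan as written leads to a wrong conclusion. The 6.3-11.0% requires an analyst to run both scales and keep the better one. The protocol names ml as the unit, so a departure from it would be visible. The 6.9% and 8.6% maxima belong to an assumed grid and to a model that section 11 does not specify. Pooling of arms and legs is inferred from the plan's silence; localisation and age are recorded on day 0 and can be shown descriptively.

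Percent change of the limb has its own weakness. The hypotheses concern the malformation, and dividing a lesion's emptying by whole-limb volume makes the same emptying look smaller in a leg. Adding three ratios for two devices, plus lesion summaries and a second regression scale, would multiply results without naming a main one.

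**Conclusion.** No change to the plan follows. The comparisons with no stocking rest on within-patient signed-rank tests, which are sound on either scale. Which scale has more power depends on an error structure the documents do not describe (4 to 8 points one way, 6 to 20 the other). The unstated regression outcome is missing detail with a sensible default: the within-patient class difference in ml, adjusted for no-stocking volume. A confidence interval is ordinary reporting that an analyst can supply from the planned data. Percent change is optional, and its meaning depends on whether the denominator is the extremity or the malformation. What remains is a modest gap in prespecification and reporting. This conclusion would weaken if the regression scale were in fact chosen by its p-value. Every size quoted rests on assumed volumes, limb mix and error.

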**Secondary hypotheses:**

Furthermore, it is assumed that the effect of the compression therapy occurs immediately after the application of compression and has an effect on the patient's quality of life.

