## 8.2 Participant number

Approximately 25 patients with venous malformation of the upper/lower extremities, age 6-70 years are to be included. Compression in the form of individually fitted compression stockings will be applied by the patient himself or by his parents.

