## 9.2 Measurements

### *Investigation day 0*

After informing of the subjects, gender, age and localization of the venous malformation are recorded for all study participants as basic data. The measurements for the individualized preparation of class I and II compression stockings are then taken.

Between investigation day 0 and 28 participants do not wear any compression stockings.

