### ***Investigation day 56***

After four weeks of compression therapy with the first compression stocking all subjects are examined at day 56 by SF-12 questionnaire and by the questionnaire "Tragekomfortbogen" (*comfort of wearing questionnaire*). Then the therapy is continued for four more weeks with the remaining compression stocking that has not yet been worn. Even during this compression therapy the compression class is unknown to the patient and investigator.

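### SF-12: with no break at day 56, the class-wise tests against day 28 rest on an unchecked no-carryover assumption, and the class-free quality-of-life hypothesis has no test of its own

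*Combined protocol and SAP*

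**What the plan says.** The order of the two classes is randomised (sections 7.2 and 7.3). SF-12 is completed at day 28 before any study stocking is worn, at day 56 after the first stocking, and at day 84 after the second (section 9.2). A stocking-free interval precedes the baseline: "Between investigation day 0 and 28 participants do not wear any compression stockings". There is none between the classes. At day 56 the plan reads: "Then the therapy is continued for four more weeks with the remaining compression stocking that has not yet been worn". No new baseline is taken.

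Section 11 says: "Although making use of a crossover design, we do not expect any carryover or period effects due to the nature of the treatments". It then draws the consequence: "Therefore, differences between the treatments and baseline measurements are evaluated using Wilcoxon signed rank tests". For the comparison of the two classes it adds: "Moreover, linear regression analysis is used to adjust for variations in" the baseline values. It names no period or sequence term, no check of carryover and no first-period analysis.

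The quality-of-life hypothesis in section 5.1 concerns compression therapy as such: "Furthermore, it is assumed that the effect of the compression therapy occurs immediately after the application of compression and has an effect on the" (the sentence ends by naming quality of life). It does not single out a class.

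**The concern.** A paired test of class I against day 28 combines two kinds of patient. In those who start with class I, the change is day 56 minus day 28 and reflects four weeks of class I. In those who start with class II, it is day 84 minus day 28 and reflects four weeks of class II followed at once by four weeks of class I. The same holds for class II with the orders reversed.

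If nothing persists, this is harmless. If part of the first stocking's effect on SF-12 persists, it is credited to the second class and the class difference shrinks. Section 11 gives the nature of the treatments as its only reason for excluding this. That reason is easier to accept for a volume measured with the stocking on than for a patient-reported score after four weeks of wear.

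There is also a mismatch between hypothesis and test. The question is whether compression therapy changes quality of life. The plan answers it with two class-wise tests, each of which leaves out one of the patient's two on-treatment scores.

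**Working it through.** **Inputs from the plan.** About 25 patients (section 8.2), significance at p ≤ 0.05 (section 11), and SF-12 at days 28, 56 and 84. The sample size comes with no effect size, SD or power, so there is no figure to reproduce.

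**Assumptions.** Two-sided tests; 1:1 allocation of order (not stated); normally distributed changes with SD 8 or 10 points; no class I effect on SF-12; a class II effect of 3 or 5 points, of which a fraction c persists to day 84.

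**Share of class I scores that follow class II.** Balanced order gives 12/25 = 48% or 13/25 = 52%. Simple 1:1 randomisation gives 8 to 17 of 25 (32% to 68%) as the 95% range.

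**Shift in the class I mean change.** With 12 class-II-first patients and a 5-point effect, the shift is (12/25) × 5c: 1.2 points at c = 0.5 and 2.4 points at c = 1. The true value is 0.

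**False-positive rate of the class I test against day 28** (simulated Wilcoxon signed rank, n = 25, 12 class-II-first; ranges cover SD 10 to SD 8):

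| Class II effect | c = 0 | c = 0.5 | c = 1 |
|---|---|---|---|
| 5 points | about 5% | 8-10% | 18-25% |
| 3 points | about 5% | 6-7% | 10-12% |

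With 13 class-II-first patients, the 5-point rate at c = 1 is 21% to nearly 30%.

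**Class difference.** If a fraction c of each class's effect persists, the two-period estimate has expectation (1 − c/2) times the true difference, which is 75% of it at c = 0.5.

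**Precision of the class-free test.** Let s² be the error variance of one score.
- One score minus baseline: s² + s² = 2s².
- Mean of two scores minus baseline: s²/2 + s² = 1.5s².
- Reduction: 0.5/2 = 25%.

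Simulated power at n = 25 rises from about 50% to 62% for a true effect of 0.6s, and from 75% to 86% for 0.8s. If the effect varies between patients with variance s², the gain is smaller: about 37% to 42-43%, and 57% to 65-66%.

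**Cost of relying on the first period.**
- Class against baseline: the SE is larger by √(25/12) = 1.44 or √(25/13) = 1.39, so about 1.4 times.
- Class I against class II, with correlation r between scores: the squared SE ratio is (1 − r²)(1/12 + 1/13) ÷ [2(1 − r)/25], roughly 2(1 + r). The SE ratio is 1.61, 1.73 and 1.85 at r = 0.3, 0.5 and 0.7.

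**Bias against variance for the class difference** (true difference 5 points, r = 0.5, so the SD of one score equals the SD of change). The two-period RMSE is √(SD²/25 + (5c/2)²). The first-period RMSE is √(SD² × 0.75 × (1/12 + 1/13)).

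| SD | Two-period, c = 0.5 | c = 0.75 | c = 1 | First period |
|---|---|---|---|---|
| 8 | 2.03 | 2.46 | 2.97 | 2.77 |
| 10 | 2.36 | 2.74 | 3.20 | 3.47 |

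The two-period estimate has the smaller RMSE up to 75% persistence at both SDs, and at full persistence when the SD is 10.

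**The case against.** The plan can be defended on several grounds.

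**Carryover may be small.** Section 10.1 expects swelling and slight pain while stockings are off, section 4 says malformations do not regress, and section 5.1 assumes an immediate effect. This fits an effect that lasts only while the stocking is worn. SF-12 is also taken at the end of each four-week period, so a class II effect would have to outlast that stocking by four weeks. This stands as an argument that 50% to 100% persistence is a demanding range. It does not show that persistence is zero, and the plan includes no check.

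**The primary hypothesis is not touched.** A reader might infer that carryover biases the trial towards its claim that class I is sufficient. The documents do not support that. The claim in section 5.1 concerns volume, and section 9.2 has volume measured on day 28 without a stocking and with each class, before either wear period. The comfort questionnaire has no day 28 value, so the baseline test does not apply to it.

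**The direction is not fixed.** If class II lowered SF-12, persistence would work against class I.

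**First-period data are not simply better.** A reader might want them to replace the two-period class comparison. The RMSE figures speak against that over most of the assumed range. This objection stands, and it limits the first-period analysis to a sensitivity role.

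**The two-score mean has limits.** If persistence exists and the classes differ, each patient's mean still depends somewhat on order. The test remains sound for the class-free question, because without any compression effect nothing can persist. It does not remove a change since day 28 common to all patients. A common drift of 0.5 SD of the single-score change gives about 65% rejection with one score and 77% with the mean of two.

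**Conclusion.** The point holds for SF-12 only, as an improvement to a secondary analysis. The class-wise tests against day 28 are valid if section 11's assumption is true. It would go too far to say that the effect cannot be credited to class I at all: class-I-first patients give scores free of class II, and misattribution arises only if something persists. What can be said is that, under persistence, the change cannot be credited to class I alone, and that the plan would not reveal it.

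The false-positive rates of about 8-10% (half persistence) and 18-25% (full persistence), against a nominal 5%, rest on assumed values: no class I effect, a 5-point class II effect, SD of change 8 to 10, and balanced order. Pooling over orders is inferred from a paired test with no order or period term; the plan does not say so in words.

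Separately, the class-free hypothesis can be tested once with data already collected, with a variance of the change up to 25% lower.

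**What to change.** In section 11, for SF-12:

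1. Make the main test a single Wilcoxon signed rank test of each patient's mean of the day 56 and day 84 scores minus the day 28 score. This answers the hypothesis as stated and assigns no effect to the wrong class.
2. Keep the two-period class-wise results as secondary. Show them by order, add a period term to the class comparison, and add a first-period sensitivity analysis: day 56 minus day 28 within each first-assigned class, and the day 56 score regressed on class and day 28 score. The period term handles a change common to both orders but not persistence that differs by class, so the by-order display and the first-period analysis are both needed.
3. Replace the sentence that rules out carryover with a statement that its absence is assumed for SF-12.

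The cost is wording only, with no new visit or measurement. Three limits should be stated. First-period standard errors are about 1.4 times larger against baseline and about 1.6 to 1.85 times larger for the class comparison (score correlation 0.3 to 0.7). Patients without a day 84 score need a handling rule for the two-score mean. With no untreated group, none of these analyses separates the effect of compression from a change over time since day 28 shared by all patients.

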## 4 Scientific background

Vascular malformations are a rare disease with a prevalence of 1.5% in the whole population. 2/3 of peripheral vascular malformations are venous malformations, of which 40% are located at the extremities.

They develop congenitally and are characterized by growth proportional to body growth. Hormones (puberty, pregnancy), infections, operations, traumas stimulate growth. They do not show any regression tendencies.

Depending on their localization and extension, they can lead to considerable discomfort with limited physical activity and loss of quality of life.

In Germany, the therapy of venous malformations lies within the responsibility of a few specialized centers and depends on the physical impairment and subjective symptoms. In addition to interventional sclerotherapy, conservative therapy is performed in the form of compression therapy with appropriate compression stockings. To date, however, there are no study-based investigations and recommendations for this kind of therapy.

The study is intended to investigate the influence of flat-knitted compression stockings of different compression classes (class I and II) on the morphology (volume behavior) of venous malformations and to derive a therapeutic recommendation. The hypothesis is that a sufficient compression effect is already present in stockings of compression class I. We anticipate a relevant effect on the volume of the malformation under this kind of treatment. Furthermore, it is assumed that the effect of the compression therapy occurs immediately after the application of compression.

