### ***Investigation day 28***

Participants fill out the SF-12 questionnaire. Then a measurement of the volume of the affected extremity is performed by perometry and MRI. First without any compression stocking and afterwards with both individualized compression stockings of class I and II.

This is followed by a four-week treatment with one of the two compression stockings, whereby the selection of compression class will be double-blinded.

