### ***Investigation day 84***

After the four weeks lasting therapy with the other compression class, participants are examined at day 84 in the two questionnaires (SF-12 and "Tragekomfortbogen" [*comfort of wearing questionnaire*]) again.

Figure 1 shows the graphical presentation of the planned measurements as well as their chronological sequence for each subject.

[figure not shown]

Figure 1: graphical presentation of all measurements with chronological sequence for each subject

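### The direct class I versus class II comparison should be a within-patient contrast, with a period term for SF-12, instead of a baseline-adjusted linear regression (minor, cheap improvement)

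*Combined protocol and SAP*

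**What the plan says.** Section 11 gives two inferential methods. Wilcoxon signed rank tests are for differences between the treatments and baseline. The direct comparison of the classes goes to a regression: "linear regression analysis is used to adjust for variations in" "baseline measurements for the direct comparison of compression classes". No patient effect, mixed model or difference outcome is mentioned.

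Period and carryover are set aside by a declared assumption: "Although making use of a crossover design, we do not expect any carryover or period effects due to the nature of the treatments".

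The measurement schedule is in section 9.2:

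- **Volume**, all on day 28: "First without any compression stocking and afterwards with both individualized compression stockings of class I and II".
- **SF-12 baseline**, also on day 28: "Participants fill out the SF-12 questionnaire".
- **SF-12 under the first stocking**: "all subjects are examined at day 56 by SF-12 questionnaire and by the questionnaire" on wearing comfort.
- **SF-12 under the second stocking**: "After the four weeks lasting therapy with the other compression class, participants are examined at day 84 in the two questionnaires".

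The class comparison is tied to a stated question. Section 4 says the study is to investigate the "influence of flat-knitted compression stockings of different compression classes (class I and II) on the morphology (volume behavior) of venous malformations".

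**The concern.** Every patient is measured under both classes, so the natural class contrast is within the patient. The one method tied to that contrast is described only by its baseline covariate. There are two difficulties.

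1. **The adjustment cannot do what it is said to do.** A patient has one no-stocking volume and one baseline SF-12, and the same value goes with both classes. Baseline is therefore balanced exactly across class, and in complete data the class estimate is the same with or without it. If the two class values are stacked as separate rows, baseline changes only the standard error, which then ignores the pairing.
2. **For SF-12 the two classes are observed in different periods.** The reason given for expecting no period effect is the nature of the treatments. That does not address a time trend in a self-reported score. Volume is not affected, because both class volumes are taken on day 28.

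At stake is a wrong standard error for the class contrast. For SF-12 there is also lost power, and bias given the realised order split, if a sizeable period effect exists.

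Wearing comfort can be described as planned. It has no baseline, so if a class test were wanted, neither inferential method in section 11 would fit it.

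**Working it through.** **Inputs.** n = 25 (section 8.2, approximate). Alpha is 0.05 (section 11), taken as two-sided. The documents give no power, SD, correlation or period effect, so there is no planned figure to reproduce. All of the following are assumptions: equal variances; a true class effect of 0.584 SD of the within-patient difference, which gives a paired t-test 80% power at n = 25; and the correlations and period effects listed below.

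**Step 1: stacked rows.** Let rb be the correlation of each class value with baseline, rc the correlation between the two class values, and s² their variance.

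- Variance reported by a regression of the 50 rows on class and baseline: 2s²(1 − rb²)/n
- True variance of the class contrast: 2s²(1 − rc)/n
- Multiplier on the SE: √[(1 − rb²)/(1 − rc)]

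The reported SE is too large when rc > rb², too small when rc < rb², and right when they are equal. For example, rb = rc = 0.5 gives √(0.75/0.50) = 1.22, and rb = 0.8 with rc = 0.5 gives √(0.36/0.50) = 0.85. Alpha and power below are simulated.

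| rb | rc | SE multiplier | Alpha | Power (paired: 80%) |
|---|---|---|---|---|
| 0.5 | 0.5 | 1.22 | 0.018 | 68% |
| 0.8 | 0.8 | 1.34 | 0.010 | 59% |
| 0.95 | 0.95 | 1.40 | 0.008 | 55% |
| 0.5 | 0.8 | 1.94 | below 0.001 | 21% |
| 0.8 | 0.5 | 0.85 | 0.093 | not valid, alpha inflated |
| 0.9 | 0.81 | 1.00 | 0.050 | 82% |

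A regression of the within-patient difference on centred baseline keeps alpha at 0.05 and power at 80% in all these settings.

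**Step 2: period, SF-12 only.** Model the within-patient difference as class effect ± period effect + N(0, 1), with the sign set by order. Compare a paired t-test (no period term) with a regression of the difference on order coded +1/−1. Section 7.3 states no balancing of order, so simple randomisation is assumed. Averaged over the possible splits:

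| Period effect (SD of difference) | Alpha without term | Power without | Power with |
|---|---|---|---|
| 0 | 0.050 | 80% | 78% |
| 0.25 | 0.050 | 77% | 78% |
| 0.5 | 0.051 | 71% | 78% |

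Given the realised split n1:n2, the bias without the term is period effect × (n1 − n2)/25. At a period effect of 0.5 SD:

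- 13:12: bias 0.5 × 1/25 = 0.02 SD, alpha about 0.03
- 15:10: bias 0.5 × 5/25 = 0.10 SD, alpha about 0.05
- 17:8: bias 0.5 × 9/25 = 0.18 SD, alpha about 0.10

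Under Binomial(25, 0.5), a split of 15:10 or worse has probability 42%, and 17:8 or worse 11%. With the period term, alpha is about 0.05 at every split.

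**The case against.** The strongest reply is that no error in the text has been shown. Regressing the within-patient difference on centred baseline is also a linear regression, is valid, and is not excluded by the sentence. The same section uses signed rank tests, so its authors knew the data are paired. This stands as far as it goes: the loss in Step 1 arises only if rows are stacked. But the sentence leaves a valid and an invalid model equally open, and the purpose it states, adjusting the class comparison for baseline, is one that neither model can serve in complete data.

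The size has no anchor in the documents, and stacking can be harmless, as the row with rc = rb² shows. That also stands. It is a coincidence of correlations, though, and not something to rely on.

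On period, the assumption is declared, average alpha is nominal without the term, and the term pays only if the effect exceeds roughly 0.25 SD. The 17:8 result needs both a large effect and an unlikely split. All of this is right and keeps the point small.

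The class contrast is not a listed hypothesis in section 5.1 or a target in section 6, and the Wilcoxon sentence might be read to include a paired class-versus-class test. The first is true, although section 4 does ask about the two classes. The second reading is strained, because the direct comparison is attached to the regression.

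**Conclusion.** The concern holds as a minor one. The only method tied to the direct class comparison is not stated as a within-patient analysis, and its baseline adjustment cannot change the contrast. That last statement follows from the design and needs no assumed number beyond complete data.

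The size of the possible SE error depends wholly on assumed correlations. It runs from too small by about 15% to nearly double, with no error when rc = rb². For SF-12, leaving out period costs about 7 points of power at an assumed 0.5 SD effect and essentially nothing at 0.25 SD. It does not inflate alpha on average over random order.

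The Wilcoxon tests of each class against no stocking, and with them the primary hypothesis, are not touched. Confidence is medium, because a valid reading of the regression sentence exists.

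**What to change.** Replace the regression sentence in section 11 with:

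> Classes I and II are compared within patients (linear mixed model with a random patient intercept and a fixed effect of class, or equivalently the within-patient difference). For SF-12, and for wearing comfort if it yields a numeric score, a fixed effect of period is added. The class II minus class I difference is reported with its 95% CI.

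Baseline may stay as a covariate, centred if differences are modelled, but should not be described as adjusting the class contrast. The expected absence of period effects should no longer be given as the reason for the choice of tests. Keep the Wilcoxon tests of each class against baseline and the descriptive summary of wearing comfort.

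**Cost.** One or two sentences, a few lines of R and no new data. The period term uses one degree of freedom. If there is no period effect it costs under 1 point of power at a 13:12 split, about 2 at 15:10, about 6 at 17:8, and about 2 averaged over simple randomisation. It does not repair carryover.
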